#### Partner Support

12. How often during your pregnancy did your male partner support you in the following ways:

|  | Never | Rarely | Sometimes | Often |
|--|-------|--------|-----------|-------|
| 12b. Provided money for transport to the hospital?   |       |        |           |       |
| 12c. Gave you advice on remaining healthy while pregnant?                                    |       |        |           |       |
| 12d. Helped you with household responsibilities so that you could rest?                      |       |        |           |       |
| 12e. Helped you with household responsibilities so that you could attend PMTCT appointments? |       |        |           |       |
| 12f. Reminded you to take your medication  |       |        |           |       |
| 12g. Reminded you of the importance of following doctor's instructions.                      |       |        |           |       |
| 12h. Provided money to purchase medication or vitamins?                                      |       |        |           |       |
| 12i. My husband gave me encouragement throughout my pregnancy                                |       |        |           |       |
| 12j. Me and my husband prayed together for a safe pregnancy and delivery                     |       |        |           |       |

13. Did your partner attend any PMTCT appointments with you?
- a. No, he did not attend any
  - b. He attended 1
  - c. He attended 2
  - d. He attended 3 or more.
  - e. N/A, no partner.
14. If #13 was no, what were the reasons he did not attend?
- a. He was working during my PMTCT appointments \_\_\_\_\_ Yes / No
  - b. He lives or works far away \_\_\_\_\_ Yes / No
  - c. He felt unwelcomed/uncomfortable at the clinic \_\_\_\_\_ Yes / No
  - d. I did not want him to attend \_\_\_\_\_ Yes / No
  - e. He did not want to attend \_\_\_\_\_ Yes / No
  - f. He had other responsibilities \_\_\_\_\_
  - g. Other, please specify \_\_\_\_\_
15. Did your male partner provide support for your child's delivery? Please select the most accurate answer.
- a. I do not have a male partner
  - b. No, my male partner did not provide any type of support for my child's delivery.
  - c. My male partner provided funding for me to get to the hospital, but did not come himself.
  - d. My male partner escorted me to the hospital while I was in labor.
  - e. My male partner visited me in the hospital after my child was born.
  - f. My male partner both escorted me to the hospital while I was in labor AND visited me in the hospital after my child was born.

## Depression

Please check the answer that comes closest to how you have felt IN THE PAST 7 DAYS, not just today.

16. I have looked forward with enjoyment to things
  - a. As much as I ever did
  - b. A little less than I used to
  - c. Much less than I used to
  - d. Not at all
17. I have blamed myself unnecessarily when things went wrong
  - a. Yes, often
  - b. Yes, some of the time
  - c. Not very often
  - d. No, never
18. I have felt scared or panicky for no very good reason
  - a. Yes, quite a lot
  - b. Yes sometimes
  - c. No, not much
  - d. No, not at all
19. I have been so unhappy that I have been crying
  - a. Yes, most of the time
  - b. Yes, quite often
  - c. Only occasionally
  - d. No, never
20. The thought of harming myself has occurred to me
  - a. Yes, often
  - b. Sometimes
  - c. Hardly ever
  - d. Never

## Risk of Violence

For each of the following statements (21-24), choose the answer which best indicates how often each has occurred in the past 12 months.

|   | Never | Rarely | Sometimes | Frequently |
|---|-------|--------|-----------|------------|
| 21. In the past 12 months, has your partner ever insulted you or made you feel bad about yourself?                          |       |        |           |            |
| 22. In the past 12 months, has your partner ever hit you, kicked you, dragged you, or beaten you up?                        |       |        |           |            |
| 23. In the past 12 months, has your partner ever hit, kicked, dragged or beaten your child?                                 |       |        |           |            |
| 24. In the past 12 months, has your partner ever physically forced you to have sexual intercourse when you did not want to? |       |        |           |            |

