### **(b) Study Population**

The primary target population for the study is HIV-positive pregnant women.

**Inclusion criteria for HIV-positive pregnant women:** All HIV-positive women presenting for PMTCT services at study hospitals during pregnancy will be eligible for enrollment in the proposed study. Pregnant women under the age of 18 are eligible for inclusion in this study. Since Kenyan law allows pregnant women the same capacity to consent as an adult, young women under the age of 18 will be able to provide consent for themselves. Mentor mothers will take additional time with young women to ensure comprehension, emphasizing that participation is optional and not a requirement for receiving standard PMTCT/EID services for themselves or their infant.

Participants who do not own a mobile phone are also eligible for study enrollment. Investigators will not provide mobile phones to women but, rather, will evaluate the efficacy of the intervention's other components (alerts to provider for missed services) among participants without phones. Mobile phone ownership will be assessed as a mediator/moderator of intervention effectiveness.

**Exclusion criteria for HIV-positive pregnant women:** HIV-positive pregnant women will be excluded from study participation if she has any condition (including drug abuse, alcohol abuse, or psychiatric disorder) that study or hospital staff feel precludes her from providing informed consent. Capacity will be determined at the time of consent. Additionally, women who transfer care from one study site to another during their PMTCT services will be ineligible for enrollment at their new facility.

To assess mediators and moderators of HITSystem effectiveness, as well as part of the objective 4 evaluation of facility adoption, we will also interview providers at intervention and control hospitals.

**Inclusion criteria for providers:** Providers will be eligible to complete the survey if they (1) work primarily in ANC, PMTCT, CCC, laboratory, or MCH departments, (2) will have been involved in the provision of PMTCT care during the course of the study, and (3) have interacted with the HITSystem 2.1 during the course of the study (intervention sites, only).

**Exclusion criteria for providers:** Providers will be excluded from survey eligibility if they do not provide informed consent.

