**Participant surveys:** A brief enrollment survey will collect same demographic and clinical data at control sites (without HITSystem 2.1) in addition to patient-level data regarding PMTCT information, motivation, partner status and support, HIV disclosure, depression (modified Edinburgh postnatal scale), and risk of violence (both arms, Appendix 2A). Repeated surveys after delivery and 6m postpartum (for VL sample collection described in Objective 2, both arms) will include these same patient-level measures to assess any changes that may mediate or moderate intervention impact (Appendices 2B & 2C). Participants will be compensated 200 KES for completion of each survey.

**Facility assessment form** (Appendix 2D) will be completed at the beginning, mid-point and end of study implementation to assess average resource level, annual PMTCT volume, and PMTCT provider-patient ratios.

**Provider surveys:** At baseline and again at the end of the study period, providers in both arms will be asked to complete a short survey (Appendix 2E) assessing provider role/ department, level of experience, knowledge and motivation regarding current PMTCT guidelines, and barriers and facilitators to provision of complete PMTCT services. We estimate n=5 providers per site to complete the survey for a total of n=60 providers (n=30 intervention, n=30 control). Prior to completing the survey, providers will complete an informed consent (Appendix 2C). Providers will be compensated 500 KES for completion of each survey.

**Supportive Supervision Visits** will occur monthly at all sites. During these visits, Site Coordinators will provide technical assistance and retraining, review study materials (informed consent forms, surveys), and review data for completeness and accuracy. The monthly frequency of site visits approximates programmatic HITSystem 1.0 implementation support in Kenya.

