Participants will be informed of these conditions during the informed consent process and the precautions described above will be employed to mitigate any risks to participant confidentiality, privacy, and safety.

**Intimate Partner Violence (IPV).** If a case of IPV is reported during study engagement (per routine surveys including questions to assess risk and experience of IPV), the participant will be counseled on options for seeking care and referred to the nearest service provider, including referral for legal action. Participants who report IPV over the phone (via study contact or mentor mother) will be encouraged to visit the clinic for an in-person consultation and will also be offered a home visit by a mentor mother. All study staff will be trained to ask for and identify signs of IPV among pregnant and postpartum women living with HIV. Any form of IPV during the study period will be reported as an adverse event.

**Psychological Distress.** The informed consent process will be carefully designed to prepare women for the Early Infant Diagnosis testing process after they deliver and the possibility of an HIV positive diagnosis for their infants. In addition, the existing use of peer counselors to support pregnant women and mothers to consider care and treatment options for themselves and their infants, and to process their and their infant's HIV positive diagnosis will continue to be employed in the study. If additional support and follow-up services are needed, the PMTCT/EID provider will arrange for additional on-site counseling.

**Reduction of Physical pain and/or discomfort.** Dried blood spot (DBS) samples will be collected for all research-related viral load testing. Providers are most experienced with this form of blood sample collection and thus may be more proficient in collecting samples in this manner with less pain and discomfort for the participant. Training on VL testing procedures will be reinforced to minimize risk of collection errors and need for repeat sample collection.

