### Risk of Violence

For each of the following statements (27-30), choose the answer which best indicates how often each has occurred in the past 12 months

|   | Never | Rarely | Sometimes | Frequently |
|---|-------|--------|-----------|------------|
| 28. In the past 12 months, has your partner ever insulted you or made you feel bad about yourself?                          |       |        |           |            |
| 29. In the past 12 months, has your partner ever hit you, kicked you, dragged you, or beaten you up?                        |       |        |           |            |
| 30. In the past 12 months, has your partner ever hit, kicked, dragged or beaten your child?                                 |       |        |           |            |
| 31. In the past 12 months, has your partner ever physically forced you to have sexual intercourse when you did not want to? |       |        |           |            |

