## Appendix IIB. Delivery survey (within 4 weeks, Intervention and Control Sites)

### For interviewer to fill out:

Study ID: \_\_\_\_\_

Date of interview \_\_\_\_\_

Interviewer initials \_\_\_\_\_

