### Risk of Violence

For each of the following statements (15-18), choose the answer which best indicates how often each has occurred in the past 12 months

|   | Never | Rarely | Sometimes | Frequently |
|---|-------|--------|-----------|------------|
| 15. In the past 12 months, has your partner ever insulted you or made you feel bad about yourself?                          |       |        |           |            |
| 16. In the past 12 months, has your partner ever hit you, kicked you, dragged you, or beaten you up?                        |       |        |           |            |
| 17. In the past 12 months, has your partner ever hit, kicked, dragged or beaten your child?                                 |       |        |           |            |
| 18. In the past 12 months, has your partner ever physically forced you to have sexual intercourse when you did not want to? |       |        |           |            |

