#### Risk of Violence

Kuom weche gi chakre (19-22), ), yier duoko manyiso kaka gik moko osetimre kuom dweche 12 mosekalo.

|  | Podi | Ok Ahinya | Seche Moko | Ngenyne |
|--|------|-----------|------------|---------|
| 21. Kuom dweche 12 mosekalo, be jaherani ose yanyi kata miyi mondo iwinj marach ne in iwuon? |      |           |            |         |
| 22. Kuom dweche 12 mosekalo , be jaherani ose goyi, gweyi,ywayi piny kata rodhi?             |      |           |            |         |
| 23. Kuom dweche 12 mosekalo , be jaherani ose goyo, gweyo,ywayo piny kata rodho nyathini?    |      |           |            |         |
| 24. Kuom dweche 12 mosekalo, be jaherani osechuni mondo uriwru kode to ne ok idwa.?          |      |           |            |         |

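### The partner-violence items use a 12-month recall at all three surveys with no incident timing, so positive follow-up answers cannot reliably separate study-period violence or change from earlier violence

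*Combined protocol and SAP*

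**What the plan says.** The Risk of Violence block in Appendix IIA (enrolment) asks the woman to "choose the answer which best indicates how often each has occurred in the past 12 months". Appendix IIB (delivery) repeats it: "For each of the following statements (21-24), choose the answer which best indicates how often each has occurred in the past 12 months". So does Appendix IIC (6 months postpartum): "For each of the following statements (15-18), choose the answer which best indicates how often each has occurred in the past 12 months". The four items are the same each time: insult, physical violence to the woman, physical violence to her child, and forced sex. Each is answered on four levels from Never to Frequently. The Swahili and Luo forms use the same period; the Luo delivery form, for example, has "Kuom dweche 12 mosekalo, be jaherani ose yanyi". No version asks for a date or whether the incident followed enrolment.

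The plan puts the answers to two uses.

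- Procedures and Data Management, Participant surveys, lists risk of violence among the enrolment measures and says that the repeat surveys "will include these same patient-level measures to assess any changes that may mediate or moderate intervention impact".
- Section 8.0, Intimate Partner Violence, names the routine surveys as a way in which a case may come to light, and states: "Any form of IPV during the study period will be reported as an adverse event".

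**The concern.** Both uses need to know when the violence happened. The adverse-event rule covers the study period only. Assessing change needs successive measurements that do not largely describe the same months. A fixed 12-month recall repeated at intervals shorter than 12 months gives neither directly.

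Partner violence matters in this trial because Section 8.0 itself recognises the risk that home visits could disclose a woman's HIV status, and the intervention-arm survey items ask whether an SMS led someone to discover it. If survey answers are taken at face value, violence from before enrolment may be logged as a study-period event. Conversely, new violence in a woman who was already positive at enrolment may be put down to her history.

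**Working it through.** The plan gives no figure to reproduce. The check is arithmetic on the recall windows.

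**Inputs from the documents**
- Recall: 12 months at each survey (Appendices IIA, IIB, IIC).
- Enrolment: any time in pregnancy. Section 5.0(b) says "All HIV-positive women presenting for PMTCT services at study hospitals during pregnancy will be eligible for enrollment in the proposed study".
- Delivery survey: 0 to 4 weeks after birth, from the Appendix IIB title, "Delivery survey (within 4 weeks, Intervention and Control Sites".
- Postpartum survey: taken with the postpartum viral load sample (Section 6.0). The 6-month form implies about 6 months, and Objective 2 allows late samples up to 7 months.

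**Assumptions**
- Gestational age at enrolment is not given; 6 to 36 weeks is used.
- Birth at 40 weeks.
- 12 months = 52.18 weeks, 6 months = 26.09 weeks, 7 months = 30.44 weeks.

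**Step 1. Recalled weeks that precede enrolment.** For enrolment at gestational week g and a survey s weeks after birth:

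pre-enrolment weeks = max(0, 52.18 − (40 + s − g))

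For example, g = 20 and s = 4 gives 52.18 − 24 = 28.2 weeks, or 54% of the window.

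| Enrolment week | Delivery survey, s = 0 | Delivery survey, s = 4 | 6-month survey, s = 26.09 | 6-month survey, s = 30.44 |
|---|---|---|---|---|
| 6 | 18.2 (35%) | 14.2 (27%) | 0 | 0 |
| 12 | 24.2 (46%) | 20.2 (39%) | 0 | 0 |
| 20 | 32.2 (62%) | 28.2 (54%) | 6.1 (12%) | 1.7 (3%) |
| 28 | 40.2 (77%) | 36.2 (69%) | 14.1 (27%) | 9.7 (19%) |
| 36 | 48.2 (92%) | 44.2 (85%) | 22.1 (42%) | 17.7 (34%) |

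**Step 2. Can the delivery window ever lie wholly inside the study?** Take the longest conceivable interval: enrolment at week 0, birth at 42 weeks, survey 4 weeks later. That is 46 weeks, and 52.18 − 46 = 6.2 weeks still precede enrolment. So it cannot.

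**Step 3. Where the 6-month window opens.** 40 + 26.09 − 52.18 = 13.9 weeks' gestation for a survey at 6 months; 40 + 30.44 − 52.18 = 18.3 weeks for one at 7 months. Women enrolled before that point have a window wholly inside the study.

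**Step 4. Overlap of the delivery and 6-month windows.** Overlap = 52.18 − weeks between the two surveys.
- Smallest: 52.18 − 30.44 = 21.7 weeks (42%).
- Largest: 52.18 − (26.09 − 4) = 30.1 weeks (58%).

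An incident in the overlap can be reported at both surveys.

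**The case against.** The strongest reply is that the enrolment survey already covers the full 12 months before enrolment, so any pre-enrolment time inside a later window has been asked about once. If answers are accurate, Never at enrolment followed by a positive answer places the violence after enrolment. With four items on four levels, a new type of violence or a rise in frequency can also be seen. This stands. A reader might infer that the surveys cannot show change or study-period violence at all, or that new violence in previously exposed women is invisible; the documents do not support either. The difficulty is concentrated in women already positive on the same item at enrolment, for whom a frequency shift across overlapping windows is only a weak signal.

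Second, Section 8.0 does not say that a positive 12-month answer is automatically counted as an adverse event. It also provides for telephone reports with in-person follow-up and for staff trained to ask about and recognise violence, and Section 6.0 keeps adverse events in study logs. This also stands: misclassification is a risk the forms leave open, not something the plan prescribes.

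Third, violence is not a primary or secondary outcome under Objective 1 or Objective 2, and it is absent from the individual-level change factors named in the Objective 1 analysis. A reader might infer that a between-arm comparison of violence is biased toward no difference, but no such comparison is specified.

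Fourth, replacing the 12-month stem with one that starts at enrolment would create its own problem. Time from enrolment to the delivery survey runs from 4 weeks (g = 36, s = 0) to 38 weeks (g = 6, s = 4). Set against a 12-month baseline, those shorter and unequal periods would produce an artificial fall in violence. This is a good reason to keep the existing items and add to them.

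**Conclusion.** The concern holds as a limitation of the instruments. Every delivery-survey window includes pre-enrolment time: 14 to 48 of 52 weeks for enrolment at 6 to 36 weeks' gestation. The 6-month window includes 0 to 22 such weeks and is free of them only for women enrolled before about 14 to 18 weeks. The delivery and 6-month windows overlap by 22 to 30 weeks. Positive follow-up answers therefore cannot, by themselves, reliably separate study-period violence or change from earlier violence, and one incident can be reported twice. The consequences fall on survey-reported adverse events and on the mediator and moderator use of the measure; no primary outcome is affected.

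The ranges rest on the assumed gestational ages and birth at 40 weeks. That the delivery window reaches before enrolment does not depend on them (Step 2).

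Two further inferences should be resisted. One is that the 6-month window reaches before enrolment for most women: the documents give no distribution of gestational age at enrolment, so that share is unknown. The other is that one incident 2 months (8.7 weeks) before a mid-pregnancy enrolment is recalled at all three surveys. For enrolment at 20 weeks it lies 46.1 + 8.7 = 54.8 weeks before a 6-month survey, outside the window. It would be recalled at all three only for enrolment from about 23 weeks (13.9 + 8.7 = 22.6), or about 27 weeks with a survey at 7 months (18.3 + 8.7 = 27.0).

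**What to change.** Keep the four 12-month items unchanged in all three surveys so that the frequency scale stays comparable. In the English, Swahili and Luo versions of Appendices IIB and IIC, add one question after each positive answer:

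- Appendix IIB: whether any such incident has occurred since enrolment in the study.
- Appendix IIC: whether any such incident has occurred since the last completed study survey. For a woman who missed the delivery survey this reaches back to enrolment, so no period is left uncovered.

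State in Section 8.0 that this field decides whether violence reported in a survey is classified as a study-period adverse event. State in the Objective 1 and 2 analysis text that any assessment of change in violence uses the field, and that it is not simply subtracted from the 12-month baseline, because the periods it covers differ between women. Flag surveys completed without the field and analyse them separately.

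The cost is a small instrument amendment in three languages and one extra field per positive answer. Surveys already completed will lack the field, so the limitation remains for those women.

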## PMTCT Knowledge

25. Can a mothers help prevent HIV transmission to her infant in the following ways?
  - a. Taking all prescribed ARTs during pregnancy and breastfeeding.....Yes / No / DK
  - b. Delivering in a health care facility, instead of at home.....Yes / No / DK
  - c. Using infant formula when it is available and breastfeeding when it is not.....Yes / No / DK
  - d. Giving the infant Nevirapine.....Yes / No / DK
  - e. Giving the infant Cotrimoxazole.....Yes / No / DK
  - f. Giving baby cow's milk and eggs before 6 months of age to help him/her grow strong...Yes / No / DK
26. It is recommended that my infant receives his/her first HIV test
  - a. Within 2 weeks of birth
  - b. At 6 weeks of age
  - c. At 6 months of age
  - d. At 12 months of age

- e. One s/he stops breastfeeding
- f. Don't know

27. It is recommended that babies continue being routinely tested for HIV until when:

- a. 6 months of age
- b. 12 months of age
- c. 18 months of age
- d. 2 years of age
- e. The baby stops breastfeeding

